8.1.6. Analysis of Immunogenicity Data

ADA status (positive/negative), ADA titer when ADA positive and potential drug interference in the assay when ADA negative (yes/no) will be listed by treatment group and time point. ADA status and potential drug interference will be also summarized.

8.1.7. Analyses of Safety Data

All safety analyses will be performed using the safety analysis set. Subjects will be analyzed according to the randomized treatment. All safety data collected on or after the first dose of IMP administration up to the last follow-up visit after the last dose of IMP, unless specified otherwise, will be summarized by treatment group according to the planned IMP. Clinical safety will be addressed by assessing AEs, laboratory assessments, physical examinations, vital signs, and 12-lead ECGs. Special attention will be paid to ISRs.

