7. STATISTICAL METHODS

All statistical methods will be detailed in a statistical analysis plan (SAP). All relevant data collected in this clinical study will be documented using summary tables, figures, and subject data listings.

An interim analysis may be performed when approximately 50% of subjects have reached the end of treatment period. The primary analysis includes all subjects that have completed their Day 57 visit or discontinued earlier. The final clinical study report (CSR) will be written at the end of the trial.

The SAP will be prepared before the first interim analysis starts. Any deviations from the protocol are to be justified in the SAP.

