7.3.8. Analyses of Safety Data

All safety analyses will be performed using the Safety Analysis Set (Section 7.2.5). Subjects will be analyzed according to the treatment they actually received. All safety data collected on or after the first dose of IMP administration up to the last follow-up visit after the last dose of IMP, unless specified otherwise, will be summarized by treatment group according to the IMP received. Clinical safety will be addressed by assessing AEs, laboratory assessments, physical examinations, vital signs, and 12-lead ECGs. Special attention will be paid to ISRs.

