1. INTRODUCTION

This is a Phase II study to assess safety, tolerability and pharmacokinetics/exposure of MOR106.

The statistical analysis described by this analysis plan will be composed by tables, listings and figures (TLFs) presented in the following analysis parts:

- General subject information.
- [REDACTED]
- Pharmacokinetics (PK).
- Immunogenicity (ADA).
- Pharmacodynamics (PD) ([REDACTED])
- Safety (adverse events, laboratory, electrocardiogram (ECG), vital signs and physical examination sections).

As a consequence of early termination of the development of MOR106 in atopic dermatitis for futility at the time point of MOR106-CL-201 interim analysis, this SAP constitutes an accordingly adapted version in terms of statistical evaluations of efficacy and pharmacodynamics endpoints.

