4.1. CONSIDERATION OF THE PLANNED VERSUS THE ACTUAL TREATMENT

The treatment group as assigned by the randomization will be used in all analyses (i.e., as-randomized analysis) except the PK analyses where the actual treatment will be used. Cross-treated subjects will be listed separately.

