8.2.1. Changes before Database Lock and Justification

Per Sponsor's decision:

- ECG parameters normal ranges will be different to the ones mentioned in protocol to be consistent with other Sponsor's studies.
- For laboratory statistical analyses, CTCAE version 4.03 will be used instead of version 5.0 to be consistent with other Sponsor's studies.
- FAS population definition will be updated to be the same as the safety analysis set (due to the type of subjects and disease, it is not anticipated to have a difference between these populations).
- The safety analyses will be based on the randomized treatment and not on the actual treatment (cf. section 7.3.8 of the protocol).

As a consequence of early termination of MOR106 development in atopic dermatitis:

- Per Protocol analysis set will not be defined as no analyses will be performed on this set.
- The Primary Analysis will not be conducted as mentioned in the protocol.
- [REDACTED]
- [REDACTED]
- [REDACTED]
- Time-to-event analysis will not be performed
- [REDACTED]
- [REDACTED]

- [REDACTED]
- Terminal half-life $t_{1/2}$ will not be derived as mentioned in the protocol.
- [REDACTED]

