14.1.7. Calculation of Percentages

The denominator for all percentages will be the total number of subjects in each treatment group within the analysis period.

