14.1.8. Tables

Analysis periods will be replaced by their respective treatment via the randomization list (i.e., an as-randomized allocation) in all tables and listings.

Table 14.3.1.1: Treatment-emergent adverse events: Summary table

Tabulation per treatment group of the incidence of subjects:

- With at least one treatment-emergent adverse event (TEAE);
- With at least one serious TEAE;
- With at least one ISR;
- With at least one skin related TEAE;
- With at least one ISR (Grade 3 or higher) or skin related TEAE;
- With at least one AE leading to death;
- With at least one mild TEAE as worst intensity per treatment;
- With at least one moderate TEAE as worst intensity per treatment;
- With at least one severe TEAE as worst intensity per treatment;
- With at least one life threatening TEAE as worst intensity per treatment;
- With at least one fatal TEAE as worst intensity per treatment;
- With at least one TEAE considered related to study drug;
- With at least one TEAE for which the study drug was temporarily stopped;
- With at least one TEAE for which the study drug was permanently stopped.

Population: safety analysis set.

Table 14.3.1.2: Treatment-emergent adverse events up to 30 days after last dose: Summary table

Same as [Table 14.3.1.1](#), but restricted to events that started after start of study medication and up to 30 days after last dose.

Population: safety analysis set.

Table 14.3.1.3: Treatment-emergent adverse events: Tabulation of all adverse events

Incidence of subjects tabulation per treatment group of TEAE classified per system organ class and preferred term.

Population: safety analysis set.

Table 14.3.1.4: Treatment-emergent adverse events up to 30 days after last dose: Tabulation of all adverse events

Same as [Table 14.3.1.3](#), but restricted to events that started after start of study medication and up to 30 days after last dose.

Population: safety analysis set.

Table 14.3.1.5: Treatment-emergent adverse events: Tabulation of all adverse events by preferred term

Incidence of subjects tabulation per treatment group of TEAE classified per preferred term.

Population: safety analysis set.

Table 14.3.1.6: Treatment-emergent adverse events up to 30 days after last dose: Tabulation of all adverse events by preferred term

Same as [Table 14.3.1.5](#), but restricted to events that started after start of study medication and up to 30 days after last dose.

Population: safety analysis set.

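### The SAP groups safety results, including the primary-endpoint AE tables, by randomized instead of received treatment and omits the reason the protocol requires

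*SAP*

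**What the plan says.** Protocol section 7.3.8: "Subjects will be analyzed according to the treatment they actually received". It also has safety data summarized by the product received.

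SAP section 8.1.7 reverses this: "Subjects will be analyzed according to the randomized treatment", with summaries by the planned product. SAP section 4.1 sets the general rule: "The treatment group as assigned by the randomization will be used in all analyses (i.e., as-randomized analysis) except the PK analyses". SAP section 14.1.8 applies it to adverse events: "Analysis periods will be replaced by their respective treatment via the randomization list (i.e., an as-randomized allocation) in all tables and listings". SAP section 14.1.7 fixes the denominators accordingly: "The denominator for all percentages will be the total number of subjects in each treatment group within the analysis period".

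The change is recorded in SAP section 8.2.1: "The safety analyses will be based on the randomized treatment and not on the actual treatment". The entry cites protocol section 7.3.8 and stops there. Protocol section 7 sets the standard for such entries: "Any deviations from the protocol are to be justified in the SAP".

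Cross-treated subjects are to appear in Listing 16.2.5.2, and Listing 16.2.1.1 flags differences between planned and actual groups. No safety table or figure by treatment received is planned.

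**The concern.** The incidence and severity of TEAEs, SAEs and AESIs are the primary endpoint, so this rule decides which arm an event is counted in for the main result. It also governs Figure 14.3.1.1, which orders preferred terms by risk difference versus placebo. A subject who received the other arm's product throughout would have every event tabulated under a treatment not taken. For a subject cross-treated for part of the period, this applies only to the affected part. PK outputs use actual treatment, so the same subject could sit in one arm for PK and in the other for safety.

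The placebo arm is planned at 20 subjects, so one subject is 1/20 = 5 points of that column. If a placebo-randomized subject receives MOR106 and then has an event, as-randomized grouping lowers the apparent MOR106 risk and raises the apparent placebo risk.

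The missing reason matters because the reader cannot tell whether the sponsor expected no cross-treatment or had another ground.

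**Working it through.** **Text comparison.** SAP section 8.2.1 lists four changes under the sponsor's decision:

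- ECG normal ranges: reason given (consistency with the sponsor's other studies).
- CTCAE version for laboratory data: same reason given.
- FAS definition: reason given (no difference from the safety set anticipated).
- Safety grouping: no reason given.

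Naming the sponsor as decision-maker says who decided, not why. Early termination does not fill the gap. The entry lies outside the list of termination-driven changes, and SAP section 1 describes the SAP after termination as an "adapted version in terms of statistical evaluations of efficacy and pharmacodynamics endpoints".

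**The plan's own figure.** Protocol section 7.1 gives an 87% probability of seeing at least one event among 40 MOR106 subjects at 5% incidence. 1 − 0.95^40 = 0.8715, so it reproduces. It presumes 40 subjects who received MOR106. If k of the 40 assigned received only placebo, 1 − 0.95^(40−k) gives 86.5%, 85.8% and 85.0% for k = 1, 2 and 3.

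**Size if cross-treatment occurs.** The arms of 40 and 20 come from the protocol. The numbers of cross-treated subjects and events are assumptions. RD is MOR106 minus placebo in percentage points, with Miettinen-Nurminen 95% intervals, the method SAP section 14.1.9 names.

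*Case A: one placebo-randomized subject given MOR106, with the event on or after the first MOR106 dose.*

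| MOR106 events | Other placebo events | As received | As randomized | Change |
|---|---|---|---|---|
| 4 | 0 | 4/41 vs 0/19: 9.8 (−7.9 to 22.7) | 3/40 vs 1/20: 2.5 (−17.1 to 16.1) | −7.3 |
| 8 | 0 | 8/41 vs 0/19: 19.5 (1.4 to 34.2) | 7/40 vs 1/20: 12.5 (−8.1 to 28.3) | −7.0 |
| 12 | 0 | 12/41 vs 0/19: 29.3 (10.8 to 44.6) | 11/40 vs 1/20: 22.5 (1.1 to 39.3) | −6.8 |
| 8 | 2 | 8/41 vs 2/19: 9.0 | 7/40 vs 3/20: 2.5 | −6.5 |

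If that subject's event is the only one, 1/41 vs 0/19 (+2.4) is displayed as 0/40 vs 1/20 (−5.0), and the sign reverses.

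*Case B: same error, no event in that subject.* For 8 events, 8/41 vs 0/19 becomes 8/40 vs 0/20 = 20.0, a change of +0.5. For 4 and 12 events the change is +0.2 and +0.7.

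*Average of A and B.* If the 8 events fall at random among the 41 exposed subjects, the expected as-randomized RD is (8/41)(12.5) + (33/41)(20.0) = 18.5, against 19.5 as received, a shift of about −1.0. For 4 and 12 events it is about −0.5 and −1.5.

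In general, with k MOR106-assigned subjects given only placebo and j placebo-assigned subjects given MOR106, the expected RD is multiplied by 1 − k/40 − j/20. That is 0.95 for k = 0, j = 1; 0.925 for k = j = 1; and 0.775 for k = j = 3.

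*Case C: one MOR106-randomized subject given placebo, 8 events in all.* If as-received grouping places anyone with at least one MOR106 dose in the MOR106 group, nothing changes unless every dose was wrong. If every dose was wrong:

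- No event in that subject: 8/39 vs 0/21 (20.5) becomes 8/40 vs 0/20 (20.0), a change of −0.5.
- Background event in that subject: 7/39 vs 1/21 (13.2) becomes 20.0, a change of +6.8.

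*No cross-treatment:* the change is exactly 0.

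**The case against.** The SAP makes the change openly: it names the protocol section replaced, records the change as made before database lock and applies it consistently, so nobody could misread the rule. No cross-treated subject is documented. Central IWRS allocation, on-site injection by designated unblinded staff and only four dosing days make full cross-treatment unlikely. The listings identify affected subjects and no event is lost, so a reader could regroup by hand. Safety analysis is descriptive under SAP section 14, so an interval that moves across zero carries no test decision. The 7-point shift is a selected case, and the average is nearer 1 point. Protocol section 7.3.8 is itself silent on mixed exposure, so restoring it alone leaves a gap.

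Most of this stands and limits the size of the point. The argument from SAP section 1 should also not be pressed far: the termination list in 8.2.1 drops the PK half-life and the primary analysis too, so that section is not a strict boundary. The safety entry's position outside the list is the firmer evidence.

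None of it supplies the reason the protocol asks for. A low probability of error does not explain replacing the protocol's rule, and the listings leave the primary-endpoint tables and the figure as they are.

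**Conclusion.** The concern holds. The SAP replaces the protocol's as-received rule for the primary-endpoint safety outputs without the justification the protocol requires. If cross-treatment occurs, the tables and figure will not describe the treatment received.

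The effect is conditional: zero with no cross-treatment, about 1 point on average for one placebo-randomized subject given MOR106 with 8 events, and about 7 points if that subject has the event. These sizes rest on the planned arms of 40 and 20 and on assumed event counts, and the intervals are descriptive only. It should be fixed, mainly because the remedy is cheap and the endpoint is primary.

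**What to change.** **Preferred: restore protocol section 7.3.8 for safety.**

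- SAP 4.1: except safety as well as PK from the as-randomized rule.
- SAP 8.1.7: refer to treatment and product received instead of randomized and planned.
- SAP 14.1.8: change to as-received allocation.
- SAP 8.2.1: delete the safety-grouping entry.
- Before unblinding, state how mixed exposure is classified. One option is that any MOR106 dose places the subject in the MOR106 group, with events before the first such dose flagged.
- Put the exposure tables (8.1.7.1, 9.8.2) on the same grouping, and footnote any denominator difference from disposition and demographics, for example 41/19 against 40/20. SAP 7.6 already requires denominators in footnotes.
- Keep efficacy as randomized and keep both listings.

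**Minimum: keep the as-randomized rule, state the reason in 8.2.1, and add the AE tables and Figure 14.3.1.1 by treatment received if any cross-treatment occurs.**

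The preferred fix costs a few wording edits, one classification rule, footnotes and minor programming, since PK already needs the actual-treatment grouping. The minimum costs one sentence, plus outputs produced only if needed.

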8.1.7.1. Extent of Exposure

A subject's extent of exposure to IMP will be generated from the IMP administration page of the CRF. Extent of exposure data will be summarized by treatment group. Extent of exposure to IMP will be expressed as the number of days between the first and last dose of IMP, inclusive, regardless of temporary interruptions in IMP administration and summarized by treatment group.

In addition, the number (percentage) of subjects who received all four treatment days, only three treatment days, etc. will also be summarized.

8.1.7.2. Adverse Events (AEs)

Clinical and laboratory AEs will be coded using the latest version of the Medical Dictionary for Regulatory Activities. System Organ Class (SOC), High Level Group Term, High Level Term, Preferred Term, and Lower-Level Term will be attached to the clinical database.

The following AEs will be considered as TEAEs:

- All events during the complete study, with an onset on or after the IMP start will be counted.

Summaries (number and percentage of subjects and the number of events) of TEAEs by SOC and Preferred Term will be provided by treatment group. Subjects with TEAEs will also be summarized by causal relationship to IMP and severity. In addition, ISRs, skin related AEs, TEAEs leading to premature discontinuation of IMP and SAEs (including the non-treatment-emergent SAEs) will be summarized and listed.

Additionally, selected tables will also be created restricted to events with an onset date on or after the IMP start date and up to 30 days after last dose of IMP.

8.1.7.3. Clinical Laboratory Evaluations

Laboratory assessments will be analyzed descriptively. Changes from baseline (Day 1 pre-dose) and shifts according to normal ranges and CTCAE grades will be presented as well. Analyses will be done per treatment group.

8.1.7.4. Physical Examinations

Only abnormal post-baseline physical examination results will be listed.

8.1.7.5. Vital Signs

Vital signs will be analyzed descriptively. Changes from baseline (Day 1 pre-dose) and shifts according to normal ranges will be presented as well. Analyses will be done per treatment group.

8.1.7.6. 12-Lead Electrocardiogram

12-lead ECG will be analyzed descriptively. Changes from baseline (Day 1 pre-dose) and shifts according to normal ranges will be presented as well. Frequency analyses of subjects with a prolongation of more than > 60 ms change from baseline; > 500 ms for QT, QTcF and QTcB will be presented as well (for each parameter separately). Analyses will be done per treatment group.

8.1.7.7. Other Safety Assessments

Summary statistics for ISRs and skin related AEs are described in section [8.1.10.2](#).

8.1.8. Pharmacokinetic Analyses

For subjects in the PK analysis set, individual serum concentrations of MOR106 will be listed. Descriptive statistics will be calculated by day for the serum concentrations. Mean (\pm standard error) serum concentrations of MOR106 versus time will be plotted using both linear and semi-logarithmic scales.

MOR106 serum levels will be analyzed using population PK analyses, which will be described and reported separately.

8.1.9. Pharmacodynamic Analyses

PD data will only be listed using the subjects in the safety analysis set.

8.1.10. Additional Statistical Considerations

NAP.

8.2. CHANGES TO THE PLANNED ANALYSES, NOT COVERED BY THE PROTOCOL OR BY PROTOCOL AMENDMENTS

8.2.1. Changes before Database Lock and Justification

Per Sponsor's decision:

- ECG parameters normal ranges will be different to the ones mentioned in protocol to be consistent with other Sponsor's studies.
- For laboratory statistical analyses, CTCAE version 4.03 will be used instead of version 5.0 to be consistent with other Sponsor's studies.
- FAS population definition will be updated to be the same as the safety analysis set (due to the type of subjects and disease, it is not anticipated to have a difference between these populations).
- The safety analyses will be based on the randomized treatment and not on the actual treatment (cf. section 7.3.8 of the protocol).

As a consequence of early termination of MOR106 development in atopic dermatitis:

- Per Protocol analysis set will not be defined as no analyses will be performed on this set.
- The Primary Analysis will not be conducted as mentioned in the protocol.
- [REDACTED]
- [REDACTED]
- [REDACTED]
- Time-to-event analysis will not be performed
- [REDACTED]
- [REDACTED]

- [REDACTED]
- Terminal half-life $t_{1/2}$ will not be derived as mentioned in the protocol.
- [REDACTED]

8.2.2. Changes after Database Lock and Justification

Any planned analyses made after database lock will be documented in the CSR with a justification.

9. ANALYSIS OF GENERAL SUBJECT INFORMATION AND DEFINITION OF ANALYSIS TLFS

The analysis of general subject information will be descriptive. No inferential statistics will be computed.

9.1. SUBJECT DISPOSITION

Table 14.1.1.1: Subject disposition: Analysis populations

Tabulation per treatment group (and over all subjects) of the number of subjects in each of the analysis populations (screened, randomized, safety/immunogenicity, FAS and PK) defined for the study.

Population: all screened subjects.

Table 14.1.1.2: Subject disposition: Tabulation by country and site

Tabulation per treatment group (and overall) of the number of subjects in each of the countries and sites.

Population: all randomized subjects.

Table 14.1.1.3: Subject disposition: Tabulation of the number of subjects at each time interval

Tabulation per treatment group (and over all subjects) of the number of subjects in each visit/time interval.

Population: safety analysis set.

Table 14.1.1.4: Subject disposition: Study and treatment completion and discontinuation

Table per treatment group (and overall) of completion/discontinuation from study and from study medication and the reason for discontinuation.

Population: safety analysis set.

Table 14.1.1.5: Subject disposition: First and last dates in the study

Summary showing these key dates (regardless of treatment assignment):

- Date of the earliest ICF signed for this study;
- Date of first and of last screening visit (visits as reported in the database);
- Date of first study drug administration;
- Date of last physical visit performed in this study;
- Last date of contact with any subject in this study.

Population: all screened subjects.

Listing 16.2.1.1: Subject disposition: Randomization

Listing per subject showing subject number, ICF date, randomization number, randomization groups, randomization date and time and any information on code breaking:

- the reason for blind broken
- the number of days since first study dose of study medication at the time the subject is unblinded
- the AE preferred term (in case the unblind was due to an AE)
- (verbatim) explanation on the unblinding reason.

Discrepancies between planned and actual randomization groups will be flagged.

Population: all randomized subjects.

Listing 16.2.1.2: Subject disposition: Listing by country and site

Listing per treatment arm showing the country name, the site number and the list of subjects screened at this site.

Population: all randomized subjects.

Listing 16.2.1.3: Subject disposition: Number of days in study

Listing per treatment group, per subject and per time point showing subject number, the analysis populations inclusions, the actual study day of each visit and the whole study duration.

The whole study duration is derived as last date of contact – date of ICF + 1 day.

Population: safety analysis set.

Listing 16.2.1.4: Subject disposition: Study and treatment completion and discontinuation

Listing per treatment group and per subject showing the study completion or discontinuation status, the number of days since first study treatment administration at study termination and the subject's date of last contact in study. In case of discontinuation, the related reason and any available specifications will also be printed (i.e. the AE reported terms if the discontinuation was due to an AE, etc.).

The treatment completion or discontinuation status will be listed in a similar way.

Population: safety analysis set.

Listing 16.2.1.5: Subject disposition: Study analysis periods

Listing per treatment group and per subject showing the analysis periods, including the start and end dates of each analysis period and the date of first and last study drug administration.

Population: safety analysis set.

